[¥]The baseline high resolution, contrast-enhanced CT scan (2mm or less slice spacing) performed within three months prior to enrollment will be reviewed by the independent core lab for patient eligibility determination. Evaluations of endograft performance, renal stent graft patency and integrity, and stent graft patency and integrity will be made based upon post-operative CT scan evaluations by the core laboratory.

*Follow-up windows are ±2 weeks (1 month visit); ±1 month (6 month visit); ±2 months (Year 1 visit); ±3 months (Years 2 through 5 visits)

Statistical

Considerations: *Study Population:* The intent to treat (ITT) population in this study consists of all patients who are enrolled and treated.

Trial Success, Safety: The primary safety analysis is **Major Adverse Events (MAE)**, as previously defined. This analysis is limited to patients enrolled in the Trial Phase (i.e., roll-in patients are not included and will be reported as a separate feasibility group). The primary endpoint is to show that the % of patients with an MAE is statistically superior to that in the Endologix open surgical historical control group at 30 days. The hypothesis test will be evaluated by the exact test as a one-tailed test, using significance level $\alpha=0.025$. Multivariable analyses will be used to assess predictors of trial success.

Trial Success, Effectiveness: The primary effectiveness analysis is **Treatment Success**, as previously defined. This analysis is limited to patients enrolled in the Trial Phase (i.e., roll-in patients are not included and will be reported as a separate feasibility group). The primary endpoint is to show that the % of patients with Treatment Success is statistically superior to the target rate of 80% at one year. The hypothesis test will be evaluated using the exact binomial distribution as a one-tailed test, using significance level $\alpha=0.05$. Multivariable analyses will be used to assess predictors of trial success.

Additional Evaluations: Appropriate statistical methodology will be used to analyze all additional evaluations.

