6.3. ADDITIONAL EVALUATIONS

Additional evaluations include:

- **Procedural and In-Hospital Evaluations:**
 - Volume of contrast media used;
 - Fluoroscopy time;
 - Total procedure time;[‡]
 - Time in ICU;[§]
 - Estimated blood loss;
 - % requiring blood transfusion;
 - Anesthesia time;[¥]
 - Time to hospital discharge;[£]
- **Mortality**, all-cause and aneurysm-related, within 30 days, at six months, and years 1 through 5;
- **MAE Individual Components** within 30 days, at six months, and years 1 through 5;
- **Composite MAEs** after 30 days ,at six months, and years 1 through 5;
- **Aneurysm Rupture** within 30 days, at six months, and years 1 through 5;
- **Conversion to Open Repair** within 30 days, at six months, and years 1 through 5;
- **Adverse Events** (serious and non-serious) within 30 days, at six months, and years 1 through 5;
- **Distal Blood Flow** pre-discharge and at 30 days, six months, and years 1 through 5 as determined by ankle-brachial index measurements and changes over time.
- **Endograft Performance** (aneurysm sac diameter change from the first post-operative visit; device migration; incidence of endoleak) at 30 days, 6 months, and years 1 to 5;
- **Renal Function** pre-discharge and at 30 days, six months, and years 1 through 5, as assessed by the estimated glomerular filtration rate (eGFR) and changes over time;
- **Renal Stent Graft Patency and Integrity** within 30 days, at six months, and years 1 through 5, as determined by contrast-enhanced CT scan, and as assessed by the independent core laboratory, inclusive of:
 - Patent luminal flow
 - Absence of kinking, stenosis, or occlusion (>60%)
 - Absence of stent fracture
 - Absence of graft failure
 - Absence of renal infarct >30%

[‡]Elapsed time from the first break of skin to final closure (i.e., skin to skin time).

[¥]Elapsed time from the initiation to the end of the anesthesia protocol.

[§]Elapsed time from the first administration of anesthesia to release from the ICU or post-anesthesia care unit providing ICU-level care. If the patient is not admitted to the ICU, this is defined as 0 hours.

[£]Elapsed time from initiation of the procedure to physical discharge from the hospital.

- **Stent Graft (Fenestrated/Bifurcated) Patency and Integrity** within 30 days, at six months, and at years 1 through 5, as determined by contrast-enhanced CT scan, and as assessed by the independent core laboratory, inclusive of:
 - Patent luminal flow
 - Absence of kinking or occlusion

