
8.6.4. Enrollment

The investigator and the Sponsor will assure all **SCREENING AND BASELINE** CRFs are complete with no unresolved issues.

Only after the Sponsor notifies the investigator of the patient eligibility by fax with a **CONFIRM** designation is the patient to be scheduled for the procedure.

The date of study enrollment is the date that the procedure is performed, as documented on the **PROCEDURE REPORT** CRF. This date is also considered Day 0 for follow-up date calculation.

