8.7.7. Clinical Events Committee Review

Overview

The clinical events committee (CEC) identified in §2 consists of at least three physicians who will serve as independent experts responsible for evaluation and categorization of adverse events reported by the investigators in the trial. Analyses of events described in this protocol will be based on the CEC-determined categorization.

The primary purpose of these individuals is to ensure a consistent, independent review of events and their clinical significance using standardized criteria and definitions. A curriculum vita for each CEC member is maintained by Endologix, and is available for regulatory review. Due to the need for independence, these individuals may not participate in this trial as investigators, and may not hold significant material, financial or other interests which create a potential conflict with respect to this role, including but not limited to significant equity

interest in Endologix.

Process

Endologix will provide independently to the CEC the complete case report form event text that details all deaths and the events as reported by the clinical site investigators. This information will be provided without identification of the site name, and will identify patients by identification number and initials only. Non-serious events or events that are reported as clearly unrelated events will not be assessed by the CEC. The CEC will review events and any follow-up data requested from Endologix. This may include copies of such documents as progress notes, operative notes, discharge summaries, death summaries, and autopsy reports.

The CEC will document the event categorization for each event individually. Meeting notes and supporting information, requests for documentation, etc. will be maintained.

Event Definitions

The following event definitions will be applied to the Primary Endpoint Analysis during this study. Where possible, events will be categorized as being related to the endovascular procedure/bifurcated device, to the fenestrated device, or to the renal stent graft device.

- *Death*: Any death occurring during the study period, regardless of cause.

Death will be further subcategorized as early (within 30 calendar days from the date of the procedure) or late (>30 days). It will also be subcategorized as aneurysm-related or not aneurysm-related.

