Aneurysm-related death is defined as: any death occurring within 30 days from the date of the procedure, regardless of cause, and death due to aneurysm rupture or following any procedure intended to treat the aneurysm.

- *Procedural Technical Failure*: An event occurring procedurally or within 30 days post-procedurally that meets one or more of the following criteria:
 - *Aortic Stent Graft Failure* is defined as a failure of the bifurcated or fenestrated proximal extension stent graft to be delivered and deployed, such that the procedure is not completed, or the device failure results in a serious complication, or a residual Type I or III endoleak that cannot be resolved during the index procedure;
 - *Renal Stent Graft Failure* is defined as a failure of the renal stent graft to be delivered and deployed, such that the procedure is not completed, or the device failure results in a serious complication.
- *Major Adverse Event*: An event occurring during the trial that meets one of the following criteria:
 - *All-Cause Death* (see above).
 - *Bowel Ischemia*: the lack of adequate blood flow to the intestines that requires

intensification of medical therapy or surgical/endovascular intervention.

- *Myocardial Infarction*: the presence of raised levels of one or more cardiac biomarkers in comparison to laboratory reference ranges;
 - *Paraplegia*: Paralysis of the lower extremities inclusive of the lower trunk.
 - *Renal Failure*: the need for temporary or permanent dialysis or >0.5mg/dL increase in pre-operative serum creatinine level at two consecutive intervals;
 - *Respiratory Failure*: pneumonia or respiratory failure requiring ventilator support beyond 24 hours post-procedure;
 - *Stroke*: a sudden development of neurological deficit due to vascular lesions of the brain such as hemorrhage, embolism, or thrombosis that persists for >24 hours.
 - *Blood Loss >1,000cc*: Estimated blood loss during the index procedure $\geq 1,000$ cc.
- *Other Definitions*:
- *Aneurysm Enlargement*: Core Lab reported aneurysm sac diameter increase of >5mm in late follow-up as compared to the initial post-operative measurement.
 - *Aneurysm Rupture*: internal bleeding or leaking of blood from the aneurysm subsequent to the index procedure.

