10.8 ADDITIONAL EVALUATIONS

- 10.8.1 In the event that balance between the treated and control groups is not sufficiently close to allow direct comparison, a multivariable analysis will be done in which the MAE rates between the two groups will be compared with the treatment group, propensity score class, and the covariates for which balance was not satisfactorily achieved. This exploratory analysis will determine if treatment retains statistical significance in the presence of the propensity score class adjustment and covariate adjustment for those covariates unsatisfactorily balanced by the propensity score. Also, special interest will be directed to whether the covariates unsatisfactorily balanced have a statistically significant relationship to the MAE rate.
- 10.8.2 *Procedural and In-Hospital Evaluations:* The need for blood transfusion, estimated blood loss volume, contrast volume, fluoroscopy time, procedure time (and other intraprocedural times), anesthesia time and type, frequency of concomitant procedures, ICU time, and time to hospital discharge will be presented descriptively. Qualitative variables will be presented with rate. Quantitative variables will be presented with mean, standard deviation, median, minimum and maximum.
- 10.8.3 *Mortality:* The proportion of patients with mortality (all-cause and aneurysm-related) will be presented at 30 days and at each subsequent timepoint for which data are available (i.e., six months, and annually at years 1 through 5). A descriptive analysis and a Kaplan-Meier analysis of all-cause and aneurysm-related mortality through 30 days and for late follow-up including 30 days will be presented.
- 10.8.4 *Major Adverse Events (MAE) Individual Components:* The proportion of patients experiencing each category of MAE within 30 days and after 30 days at each subsequent timepoint for which data are available will be presented.
- 10.8.5 *Composite Late MAEs(after 30 days):* The proportion of patients experiencing an MAE after 30 days will be presented at each subsequent timepoint for which data are available. A descriptive analysis and a Kaplan-Meier analysis of the MAE composite will be presented for follow-up through 30 days and for late follow-up including 30 days. The descriptive analysis will present the rates for the composite MAE and each individual adverse event that is part of the composite.

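### The last limb of the aneurysm-related death definition has no time window, requires no causal link and does not exclude the index procedure

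*Combined protocol and SAP*

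**What the plan says.** Section 8.7.7 defines aneurysm-related death by three limbs:

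1. "any death occurring within 30 days from the date of the procedure, regardless of cause";
2. a death caused by rupture of the aneurysm;
3. a death after any procedure aimed at treating the aneurysm.

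Limbs 2 and 3 share one phrase: "death due to aneurysm rupture or following any procedure intended to treat the aneurysm".

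Just before this, the section splits deaths into early and late at 30 days and adds a second split: "It will also be subcategorized as aneurysm-related or not aneurysm-related". The CEC makes the classification, and the analyses rest on it.

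Section 6.3 lists mortality as an additional evaluation, "all-cause and aneurysm-related, within 30 days, at six months" and at years 1 through 5. Section 10.8.3 plans "A descriptive analysis and a Kaplan-Meier analysis of all-cause and aneurysm-related mortality through 30 days", and the same for late follow-up. No hypothesis test is attached.

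**The concern.** The first limb carries a clear 30-day limit. The third carries none, and its wording takes in any procedure, so nothing on its face removes the index implant. A committee applying the text as it stands would have to class an unrelated death in year 4 as aneurysm-related.

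At stake is whether aneurysm-related mortality after 30 days carries information beyond all-cause mortality. It also matters whether the CEC can classify late deaths the same way each time. If the rule is settled only as deaths accrue, in a single-arm trial, the choice of reading could follow the cases.

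**Working it through.** The plan states no figure on this point, so there is none to reproduce. The check is a comparison of the text, followed by a count in symbols.

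**Does every analysed patient meet the condition of limb 3?** The synopsis says: "The intent to treat (ITT) population in this study consists of all patients who are enrolled and treated". Section 10.1 bases the analysis on the attempt to implant. Section 8.6.4 says: "The date of study enrollment is the date that the procedure is performed". So every on-study death comes after the start of a procedure intended to treat the aneurysm. A death during the implant itself falls under limb 1.

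**Is limb 3 narrowed elsewhere?** No section gives it a window or a causal test. Section 8.7.7 defines a secondary procedure as an intervention after the index procedure, and defines conversion to open repair separately. The definition of aneurysm-related death uses neither term.

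**Counts under each reading.** Let

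- D = all deaths on study;
- E = deaths within 30 days of the index procedure;
- R = later deaths from rupture;
- S = other later deaths that follow a further aneurysm procedure;
- S* = the part of S that falls within 30 days of that further procedure or was caused by it.

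Then

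- literal reading: count = D, and limbs 1 and 2 add essentially nothing;
- later procedures only: count = E + R + S;
- later procedures with a window or attribution: count = E + R + S*.

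So E + R + S* ≤ E + R + S ≤ D. Relative to the last rule, the literal reading over-counts by D − (E + R + S*), and the later-procedures reading by S − S*.

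**Example deaths.**

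| Death | Literal | Later procedures only, no window | Later procedures, window or attribution |
|---|---|---|---|
| Any cause, within 30 days of implant | yes | yes | yes |
| Late rupture | yes | yes | yes |
| Cancer, year 4, no further procedure | yes | no | no |
| Endoleak embolized in year 1, cancer death in year 4 | yes | yes | no |
| Late conversion, death from its complications on day 40 after it | yes | yes | yes, by attribution |

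The third and fourth rows separate the readings. A committee member could also read limb 3 as causal, covering only deaths attributable to some procedure, which would give a further rule.

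**Where it bites.** Up to 30 days every death is in E under every reading, so the two mortality outcomes are equal there because of limb 1. The readings differ only from six months on.

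**Where it does not.** The primary safety composite in section 6.1 uses all-cause mortality. The effectiveness composite in section 6.2 has no death component. The 97 patients and the stated power come from section 10.7.2 and do not involve this definition.

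**The case against.** The best reply is that the literal reading cannot be what was meant. The index procedure has its own 30-day limb, which would be pointless if limb 3 covered it too. Section 8.7.7 requires a class of deaths that are not aneurysm-related, and sections 6.3 and 10.8.3 report the two mortality outcomes separately. A sensible committee would apply limb 3 to later procedures. A reader might infer that aneurysm-related mortality must equal all-cause mortality throughout this trial. The documents do not support that: it follows only from the literal reading, which these features argue against. This part of the reply stands.

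It does not remove the defect. On the narrower reading limb 3 still has no window and no causal test, so the embolization example still counts.

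Three further points also stand. Over-inclusion counts against the device, so the wording as printed does not flatter the result. Cause of death is recorded, autopsy is requested, and rupture, conversion and secondary procedures are each reported separately (sections 10.8.6, 10.8.7 and 10.8.15), so deaths could be reclassified from data already collected. And a bare 30-day window on later procedures would be a poor repair: it would drop the day-40 death after conversion, which the present wording captures.

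**Conclusion.** The definition needs correction. Read literally, limb 3 makes every death aneurysm-related. On the likely intended reading it still takes in unrelated deaths at any time after a secondary procedure. This is more than missing detail, because both readings put some deaths in the wrong class.

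The effect is limited to aneurysm-related mortality at six months and years 1 to 5, an additional evaluation. Trial success does not depend on it.

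The number of misclassified deaths cannot be estimated from the documents, which give no late mortality rate and no rate of reintervention followed by death. A reader might assume all-cause mortality of 5% to 8% a year and calculate 97 × (1 − 0.95^5) = 21.9 to 97 × (1 − 0.92^5) = 33.1 deaths by five years. Those rates are assumptions, loss to follow-up is ignored, and the result is D, the total of all deaths. It includes E, R and S*, which are properly classed, so it is not a count of errors.

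A reader might also infer that the wording stops the trial from showing whether repair prevents aneurysm death. A single-arm trial has no untreated comparator for that question under any definition.

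**What to change.** In section 8.7.7, keep the 30-day limb for the index procedure and replace the rest with: *death due to aneurysm rupture, or death within 30 days of, or adjudicated by the CEC as caused by, any Secondary Procedure or conversion to open repair*. This uses terms the section already defines and the window it already applies to the index procedure. The attribution clause keeps the later deaths that a bare window would lose.

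The cost is one phrase and no new data. The count may be slightly smaller than under the broad wording, and the CEC must make an attribution call for deaths more than 30 days after a later procedure. A death caused by the index implant after day 30, without rupture or a later procedure, would stay outside the definition. The sponsor should confirm that this is intended. The wording should be settled before further late deaths are classified, and any already classified should be re-read against it.

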4. TRIAL OVERVIEW

4.1. OBJECTIVE

The objective of this study is to assess the safety and effectiveness of the Endologix Fenestrated Stent Graft System for the endovascular repair of juxtarenal or pararenal (JAA/PAA) aortic aneurysms in suitable patients.

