7.4. PATIENT AND DEVICE PREPARATION

All procedures must be performed in an operating room, or in an endovascular suite having vascular surgery and anesthesia services. The Investigator will refer to institutional protocols relating to anesthesia and monitoring of vital signs.

All institutions participating in this study must utilize fixed imaging equipment during the procedure.

The appropriate length bifurcated device (22 or 25mm diameter), the appropriate Endologix fenestrated proximal extension stent graft device, and the appropriate Endologix renal stent graft devices will be selected in accordance with the patient eligibility determination. The devices will be prepared in accordance with their respective Instructions for Use. The respective Instructions for Use, inclusive of warnings and precautions, are provided in *Attachment 1*.[†]

All devices will be prepared and handled in accordance with their Instructions for Use.

Other ancillary devices will be selected by the physician per institutional standards.

[†]Accessories available and ancillary devices recommended for use during the procedure are listed in the respective IFU.

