 - *Conversion to Open Repair*: open surgical repair of the abdominal aortic aneurysm due to unsuccessful delivery or deployment of the stent graft, due to complications or other clinical situations that precluded successful endovascular treatment, or at any time following initial successful endovascular treatment for any reason.
 - *Cardiac Morbidity*: acute myocardial infarction (diagnosed based on measured levels of one or more cardiac biomarkers in comparison to laboratory reference ranges); new onset heart failure (an acute episode or exacerbation of existing low cardiac output accompanied by distal and/or pulmonary edema); intractable or malignant arrhythmia requiring cardioversion or pacemaker placement; or coronary intervention (coronary artery bypass grafting [CABG] or percutaneous coronary intervention [PCI]).
 - *Clinically Significant Device Migration*: Core Lab reported aortic stent graft movement >10mm from the original implant location resulting in an intervention or in a serious complication.
 - *Renal Dysfunction*: a reduction in the estimated glomerular filtration rate (eGFR) of >30% from the preoperative value;
 - *Secondary Procedure*: any non-diagnostic intervention after the index procedure intended to correct or repair an endoleak, limb occlusion, migration, aneurysm sac expansion and/or a device defect;
 - *Stent Graft Occlusion*: Intervention for aortic or renal stent graft occlusion or as reported by the Core Laboratory.

- *Transient Ischemic Attack*: a sudden development of neurological deficit due to vascular lesions of *the* brain such as hemorrhage, embolism, or thrombosis that persists for <24 hours.
- *Type I/III/IV Endoleak*: Core Lab reported endoleak: between the endograft and the vessel either at the proximal attachment point (Type IA) or at the distal attachment point (Type IB); between endograft components (Type III); or transgraft (Type IV)
- *Type II Endoleak*: Core Lab reported endoleak emanating from a patent collateral vessel (e.g., inferior mesenteric artery; lumbar artery; etc.).

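### A study renal stent graft that cannot be delivered and is replaced by another device can still score as technical success, and so as Treatment Success at one year

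*Combined protocol and SAP*

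**What the plan says.** Sections 6.2 and 10.7.2 make Treatment Success at one year the primary effectiveness endpoint. It requires procedural technical success and the absence of rupture, open conversion, Type I endoleak after 30 days, Type III endoleak, clinically significant migration, enlargement, and certain secondary interventions.

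Technical success has no definition of its own. Section 8.7.7 defines Procedural Technical Failure, in two parts:

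- **Aortic grafts**, three limbs. The first limb is a "failure of the bifurcated or fenestrated proximal extension stent graft to be delivered and deployed, such that the procedure is not completed". The second limb, which applies to both kinds of graft, is worded "or the device failure results in a serious complication". The third limb, which appears for the aortic grafts alone, is worded "or a residual Type I or III endoleak that cannot be resolved during the index procedure".
- **Renal stent graft**, two limbs. One is a "failure of the renal stent graft to be delivered and deployed, such that the procedure is not completed". The other is the same serious-complication limb as for the aortic grafts. There is no third limb.

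No section says when a procedure counts as completed, or how to score a study graft that is replaced by another device or left out. Section 4.1 sets the aim as to "assess the safety and effectiveness of the Endologix Fenestrated Stent Graft System", and the synopsis lists the renal stent grafts among the study devices.

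**The concern.** Failed delivery alone is not a failure of the endpoint. It must also stop the procedure from being completed or lead to a serious complication. A renal graft that cannot be delivered, is replaced by a different device, and is followed by an uneventful finish meets neither condition. Section 10.1 analyses patients by the attempt to implant, so this patient stays in the denominator and, on the plain wording, also enters the numerator. The system under test is then credited with a result that another device produced. The investigational renal component is where the wording leaves the widest gap. The margin is small: under the plan's own assumptions the expected number of successes is about two above the minimum needed.

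**Working it through.** **1. Does another component catch a replaced renal graft?**

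| Component or record | Where | Catches it? |
|---|---|---|
| Technical failure, delivery limb | 8.7.7 | No, if the procedure was finished |
| Technical failure, complication limb | 8.7.7 | No, if uncomplicated |
| Residual endoleak limb | 8.7.7 | Listed for the aortic grafts only |
| Open conversion: "open surgical repair of the abdominal aortic aneurysm due to unsuccessful delivery or deployment of the stent graft" | 8.7.7 | No, if the repair was finished endovascularly |
| Secondary procedure: "any non-diagnostic intervention after the index procedure intended to correct or repair an endoleak" | 8.7.7 | No, the substitution is made during the index procedure |
| Renal stent graft patency and integrity | 6.3, 10.8.13 | No, an additional evaluation outside Treatment Success |
| Malfunction and device-use records | 7.3 | Recorded, but not linked to the endpoint |

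Section 8.7.7 also bases event analyses on the Clinical Events Committee's categorization and keeps non-serious events from its review. An uncomplicated failed delivery may therefore never be adjudicated.

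**2. Reproduce the plan's figure.** Inputs from section 10.7.2: n = 82, null rate 0.80, planned rate 0.90, one-sided alpha 0.05. The critical count is the smallest r with P(X ≥ r | 82, 0.80) ≤ 0.05.

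- P(X ≥ 71 | 0.80) = 0.0836, too large.
- P(X ≥ 72 | 0.80) = 0.0458, so r = 72.
- Power: P(X ≥ 72 | 0.90) = 0.8057. The plan states 80.58%, so the figure reproduces.
- Enrolment: 82/0.85 = 96.5, rounded up to 97, as stated.

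**3. Direction.** Counting every non-delivery as failure can turn a success into a failure but never the reverse. The lenient count is therefore at least as high as the strict count in every data set.

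**4. Size if the strict rate is at the goal.** Let m be the assumed share of patients scored as successes who would fail on the strict count. With a strict rate of 0.80, the scored rate is 0.80 + m, and the chance of passing is P(X ≥ 72 | 82, 0.80 + m).

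| m | Scored rate | Chance of passing |
|---|---|---|
| 0 | 0.80 | 4.6% |
| 1 point | 0.81 | 7.1% |
| 2 points | 0.82 | 10.7% |
| 3 points | 0.83 | 15.5% |
| 5 points | 0.85 | 29.8% |

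**5. Size if the planned 90% is on the lenient count.** Let s be the assumed share of scored successes that were substitutions. The strict rate is 0.90 × (1 − s).

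- s = 0: 0.900, chance of passing 80.6%.
- s = 3%: 0.90 × 0.97 = 0.873, chance 52.8%.
- s = 5%: 0.90 × 0.95 = 0.855, chance 34.3%.

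**6. Margin in patients.** Expected successes at 90% are 82 × 0.90 = 73.8. At an observed 74, reclassifying 3 patients leaves 71, one below the critical count.

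**7. Other settings.** With all 97 patients the same rule needs 85 successes (attained alpha 3.5%). At a strict rate of 80%, 2 points of lenient scoring then raise the chance of passing to 9.1%, so the picture in step 4 barely changes. If the lenient rate were 95%, s = 3% leaves 0.95 × 0.97 = 0.9215, and the chance at n = 82 is still 94%.

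**The case against.** - **Omission may already be a failure.** A reader might infer that a graft left out also scores as success. The documents do not say so. Section 8.6.5 [d] lists the procedural steps whose completion is timed, and these include finishing the renal stent graft implant and flaring it. A procedure without them can fairly be read as incomplete. This stands, so omission is ambiguous rather than clearly lenient. The substitution case is stronger, because the procedure can be finished with the other device and nothing in the definition requires that a study device finish it.
- **The aortic grafts are better protected.** A reader might extend the point equally to the bifurcated and fenestrated grafts. Their delivery limb has the same wording, but residual Type I or III endoleak, open conversion after failed delivery, and the later endoleak, enlargement and reintervention components give further routes to failure. This stands, and the gap is clearest for the renal graft.
- **No document describes such cases as usual or permitted.** Section 7.4 says "Other ancillary devices will be selected by the physician per institutional standards". One might infer from this that non-study stents may replace study grafts, but the sentence follows the selection of the study grafts and says nothing about replacing them. The Instructions for Use, which might address the matter, are not in the documents reviewed.
- **The rates are assumed.** This is correct. Section 10.7.2 expects success above 90%, and at a lenient 95% the effect is small. Section 10.2 also imputes missing one-year outcomes, so 72 of 82 is the planning rule and may not be the final threshold.
- **The events would be visible.** Device use and malfunctions are recorded, and renal graft patency is reported separately. That is true, but neither changes the primary score.

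**Conclusion.** The point holds for a replaced renal stent graft. On the plain wording such a patient is a technical success, and no other component of Treatment Success corrects this. For an omitted graft the text is ambiguous, so two adjudicators could score the same patient differently in the primary endpoint.

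The direction of the effect is certain: it can only raise the measured rate relative to the strict count. Its size cannot be derived from the documents, and it would be wrong to read the figures as an established bias or to conclude that the trial's result depends on it. They show sensitivity only, under the planning rule, an assumed share of affected patients and, in the second calculation, the further assumption that the planned 90% is on the lenient count. On those terms a small number matters: 2 points of lenient scoring more than double the chance of passing at a strict rate of 80% (4.6% to 10.7%), and 3% substitutions among the planned successes take the chance on the strict count from 80.6% to 53%. This should be corrected. The plan's sample size arithmetic is not in dispute.

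**What to change.** In section 8.7.7, state that any planned study component (bifurcated, fenestrated or either renal stent graft) not delivered and deployed by the end of the index procedure is a Procedural Technical Failure, even if the procedure was finished with another device or without that component. Keep the existing serious-complication and residual-endoleak limbs. This also removes the need to interpret when a procedure is completed.

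If the primary definition must stay fixed, pre-specify in section 10.7.3 a supportive Treatment Success analysis that counts every such non-delivery as a failure.

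Either version can be scored from the Procedure Report (section 8.6.5) and the device accountability records (section 7.3), so it needs no new data collection and does not depend on which events reach the Clinical Events Committee. The rule concerns scoring only and leaves the conduct of the procedure untouched. The cost is a change of wording and possibly a slightly lower reported success rate.
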